2.7 Monitoring

The study is monitored by the core team (study chairs and medical officer) to review the renal toxicity events and HCV RNA results for evidence of virologic breakthrough, and by the ACTG Hepatitis Study Monitoring Committee (SMC) to conduct full reviews of study data. The SMC review is planned to occur at least annually, or upon request by the SMC or the study team. A formal interim review of SVR12 by the SMC is not planned, because much of study follow-up will be complete before participants reach SVR12, especially in Arm A, due to the anticipated accrual rate (5-10 per month to complete enrollment under 6 months) and the small study sample size.

2.7.1 Ongoing Team Monitoring

The core study team will review the renal toxicity events and HCV RNA results on a frequent, routine schedule. The core team will also review routinely availability of data samples for key objectives and planned assays. The study team will monitor accrual. The Study Monitoring Plan (SMP) describes team monitoring reports.

2.7.2 SMC Reviews

The SMC will review the study six months after the study enrolls its first participant, or when about 40% of the study participants (about 16 participants) have the week 16 data, whichever occurs earlier. Because Arm A treatment duration is shorter at 12 weeks, the data will include the end of treatment

data and potentially some SVR4 data from Arm A participants. The components of the SMC Review Reports as described in the SMP are outlined in Section 3.1.

2.8 General Data Analysis Considerations

- Data summaries and analyses will be completed by study arm, unless specified otherwise. They will be collapsed across treatment arms for open interim reports.
- All participants who met the study eligibility criteria and received any study treatment will be included in the planned analyses, unless specified otherwise. The participants who are found to have been ineligible for the study after enrollment occurred will not be part of the planned analyses; if any of such participants received any study treatment, their safety profiles will be described separately in an appendix to the report.
- Participants are instructed to discontinue the study prior to initiation of non-study provided HCV treatment during follow-up after discontinuation of the study-provided treatment. If they remain on study in error, the data are censored at the time of alternative HCV treatment initiation.
- For the summaries on evaluations by study visits, calculated visit weeks will be used according to the tables shown above in Section 2.6. Entry value is defined as the evaluation from the day of treatment dispensation or the closest preceding evaluation. For the post-entry values, the evaluations conducted closest to the targeted dates will be used.
- For the summaries of AEs, diagnoses and opportunistic infections, events with the onset date on or after the study treatment initiation date will be summarized.
- In data lists, study participants will be identified by an anonymous patient identifier generated at the statistical center (publicID). Dates will not be shown, but converted to time (e.g. weeks) since randomization.
- Each Table/Figure/Listing will be annotated with the name and location of the program used to create it, including its location directory.
- Key outcome measures for which analysis programs require validation and the level of validation that is required are noted throughout the plan in Section 4.

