### 9.0 STATISTICAL CONSIDERATIONS

#### 9.1 General Design Issues

A5348 is a prospective, open-label study to evaluate 12-week and 24-week regimens of LDV/SOF (Arms A and B, respectively) for the retreatment of HCV among individuals with prior treatment failures, with the addition of RBV to the 12-week regimen. It is a study to gather timely, pilot data in the retreatment of HCV in HIV-coinfected persons and to complement similar studies in HCV mono-infected persons, planned outside of the ACTG. The study will randomize the participants to the study arms, since there is clinical equipoise on the benefits and drawbacks between a shorter 12-week regimen of LDV/SOF with RBV and a 24-week regimen without RBV (see section 2.2 Rationale). The primary analysis will be conducted as a single-arm analysis for each regimen. Any comparison made between the regimens will be done as a secondary analysis. The study has not been designed to be powered for comparison between the two study regimens, and as such, any comparison needs to be interpreted with caution.

The study sample size is limited by feasibility. As a study to provide supportive data on retreatment options expeditiously in a difficult-to-treat population, the study sample size is small. Limitations inherent in most early phase studies apply. Safety and tolerability evaluations of each treatment regimen, as well as the virologic response, will inform the acceptability of each treatment regimen as a viable strategy for retreatment. Virologic outcome will be evaluated using SVR12 as the primary endpoint.

The primary analysis will be conducted as modified intent-to-treat, and all participants who meet the eligibility criteria and start study treatment will be included. The standard definition of SVR12 that is in use across the ACTG studies and, to our knowledge, the industry-sponsored studies will be used, where loss to follow-up or otherwise not evaluable for SVR12 is construed as not meeting the SVR12 response.

A5348 FINAL Version 1.0 09/29/15

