#### 9.6 Analyses

As a small study to provide supportive data on SVR12, precision is limited, and analyses related to HCV virologic response will be conducted with two-sided 90% CIs. This is noting that the lower limits of these two-sided CIs are equivalent to the limits in the 95% one-sided lower CIs. Analyses related to safety will be conducted with two-sided 95% CIs to be conservative.

The primary objective will be addressed separately in Arms A and B. The proportion of participants within each study arm who achieve SVR12 will be estimated with a two-sided Wilson CI. The analysis will be conducted as modified intent-to-treat (ITT) on participants who meet the eligibility criteria and initiate study treatment. Given the SVR12 definition, a tabulation of reasons for not achieving SVR12 (e.g., detectable HCV RNA, early treatment discontinuation, loss to follow-up) will be an important supplement to the primary analysis on SVR12. The primary analysis timeline will be driven by the last participant's completion of the SVR12 visit, rather than the study completion date. Results from the primary analysis on SVR12 may be presented publicly - for example, at a conference – prior to study database finalization that includes SVR24 completion, when SVR12 data are complete.

The secondary HCV virologic measures will also be analyzed with 90% two-sided Wilson CIs around the observed proportion in each study arm.

The SVR 4, SVR12 and SVR24 differences between the two study arms will be evaluated with 90% two-sided CIs, using the Newcomb score (Wilson) methods.

For the safety analysis, the proportion of participants with events as described in section 9.2.1.2 will be summarized with 95% Wilson CIs around the observed proportions. The worst graded event per participant over time will be used. Descriptive tables summarizing the events and the number of participants experiencing the events will be provided by grade. Descriptive summaries will also be provided on the participants who discontinue the study treatment early, categorized by the reasons for discontinuation. HIV-1 RNA statuses (<50 copies/mL) and CD4+ T-cell count changes from baseline at scheduled visits will be summarized. The summary on HIV-1 and HCV virologic failures will be descriptive, and a listing will be provided with details including time of failure and participant's ARV regimen.

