4.2.1 Adverse Events and Protocol-Required Laboratory Tests

- a) Descriptive tables summarizing the adverse events and the number of participants experiencing the events will be provided by grade and by the site report on relationship to study treatment.
- b) Summary table of all diagnoses reported.
- c) Listing of participants with renal toxicity events (defined as Grade ≥ 2 creatinine clearance post-entry or new proteinuria or glucosuria, an increase from entry glucosuria or proteinuria by $\geq 1+$).
 - baseline characteristics: age, sex, race/ethnicity, ART regimen, study treatment, cirrhosis status
 - all available results on: urinalysis protein and protein, creatinine clearance (CrCl), spot protein and creatinine (and protein/creatinine ratio)
 - study treatment modifications
 - study treatment adherence
 - ARV modifications

Notes:

1. The protocol requires grading of events according to The Division of AIDS Table for Grading the Severity of Adult and Pediatric Adverse Events, Version 2.0, November 2014, which is available on the RCC website: <http://rsc.tech-res.com/safetyandpharmacovigilance/gradingtables.aspx>
2. The protocol requires the collection of signs and symptoms, diagnoses, laboratory events that
 - a. are Grade ≥ 3 post-entry
 - b. that led to a change in treatment (excluding indications for RBV dose modification) regardless of grade, or
 - c. that met ICH, EAE or SAE guidelines regardless of grade.

In addition, all creatinine, creatinine clearance (CrCl) and urinalysis results are required. Urine spot protein and creatinine are repeated in participants who develop new proteinuria or glucosuria, an increase from entry glucosuria or proteinuria by $\geq 1+$, or who develop an increase in creatinine of 0.4 from entry or CrCl < 50 , until resolution.

3. Summary tables are based on events reported on the following forms: EVW0314, EVW0315, F2860 (Hematology), F2861 (Chemistry), LBW0144 (Creatinine Clearance) and will not explicitly include events reported on EAEs to DAIDS. Before the database is finalized, the data manager will ensure that all EAE events deemed 'reportable' and included in the SDMC AR001AES table are reflected on the study CRFs.
 4. Events with date of onset or specimen date prior to the first study treatment dose will be excluded.
 5. Deaths will be described separately and not included in the safety summary tables.

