4.3 Primary Objectives

4.3.1 SVR12

Purpose: To address the primary HCV virologic response objective to assess the proportion of participants who attain SVR12 in each study arm.

- a) Two-sided 90% confidence interval around the observed SVR proportion using the Wilson confidence limits, per protocol.
- b) Two-sided 95% confidence interval around the observed SVR proportion using Clopper-Pearson limits, to line up with the Gilead study (in consideration of joint manuscript).
- c) For the non-SVRs, reasons for failure will be provided: detectable HCV RNA after treatment discontinuation, HCV virologic failure (VF) as determined by the site, unavailable HCV RNA result, other.

Note on the primary HCV virologic endpoint:

1. SVR12 is defined in the protocol as HCV RNA < lower limit of quantification (LLOQ), either target detected (TD) or target not detected (TND), at 12 weeks after treatment discontinuation. The sample within the week R+12 visit window, as described in Section 2.6, which is closest to the targeted time will be used. If there is no HCV RNA sample within this window, then the participant will be considered SVR12 failure, unless there are preceding and subsequent HCV RNA measurements that are both <LLOQ (either TD or TND).
 2. Participants not providing SVR data (e.g. due to early study discontinuation) will be included and counted as SVR failures.
- ✓ SDAC Validation: Derivation of SVR12 variable will be validated. The analysis program that summarizes SVR12 and calculates confidence intervals will also be validated.
 - ✓ Data sources for the primary endpoint SVR12: HCVRNALDMS (LDMS data table), F1601 (off study CRF table), F4003 (off treatment CRF table), F0010 (patient visit CRF data table),

STATUS (data table on key patient characteristics and date variables including date of last dose of study treatment), CMW0029 (concomitant medication CRF table to censor data at initiation of alternate HCV treatment in case any participants erroneously remained on study when alternate HCV treatment was initiated), SPW0455 (HCV RNA specimen tracking CRF table).

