4.3.2 Safety

Purpose: To address the primary safety objective.

- a) Number of participants meeting the criteria noted below. The worst graded event per person over time will be used.
- b) Summaries on all reported adverse events and laboratory events and listings described in Section 4.2.1 provide supplemental information on safety.

Notes on the primary safety endpoint:

1. Occurrence of Grade ≥ 3 or higher adverse event (diagnosis, sign, symptom or laboratory event), SAE according to ICH criteria, or AE reported as the reason for permanent discontinuation of study treatment during study treatment and up to 30 days after study treatment discontinuation.
 2. Event that is ongoing at the same grade from prior to study treatment initiation will be excluded.
-
- ✓ SDAC Validation: The program deriving the indicator variable on meeting the safety endpoint criteria as described above will be validated.
 - ✓ Data sources for the primary safety endpoint: EVW0314, EVW0315, F2860 (Hematology), F2861 (Chemistry), HXW0148 (Signs and Symptoms History), LBW0144 (Creatinine Clearance), STATUS (data table on key patient characteristics and date variables including date of last dose of study treatment), CMW0029 (concomitant medication CRF table to censor data at initiation of alternate HCV treatment in case any participants erroneously remained on study when alternate HCV treatment was initiated).

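### Treated participants later found ineligible drop out of the primary safety count, and no all-treated SVR12 is planned beside the eligible-only result

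*SAP*

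**What the plan says.** SAP 2.8 restricts the planned analyses, unless a section specifies otherwise, to participants who were eligible and received any study treatment. It then adds: "The participants who are found to have been ineligible for the study after enrollment occurred will not be part of the planned analyses". If such a person was treated, "their safety profiles will be described separately in an appendix to the report".

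The sections that use this default are:

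- **SAP 4.3.2 (primary safety):** "Number of participants meeting the criteria noted below". No population is named.
- **SAP 4.2.1 (adverse event tables):** "Descriptive tables summarizing the adverse events and the number of participants experiencing the events will be provided by grade". The notes leave out events before the first dose and list deaths separately. They do not bring ineligible participants back.
- **SAP 4.3.1 (SVR12):** "Two-sided 90% confidence interval around the observed SVR proportion using the Wilson confidence limits, per protocol", plus a 95% Clopper-Pearson interval. The note on missing data counts those people as failures, but it does not concern ineligible participants.

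On the protocol side, 9.1 says of the primary analysis that "all participants who meet the eligibility criteria and start study treatment will be included". The SVR12 paragraph of 9.6 places the analysis "on participants who meet the eligibility criteria and initiate study treatment". The safety paragraph of 9.6 says only that "the proportion of participants with events as described in section 9.2.1.2 will be summarized with 95% Wilson CIs around the observed proportions".

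**The concern.** Whether a screening criterion was met has no bearing on whether a person was exposed to the drug. The primary safety outcome (protocol 9.2.1.2) is defined by exposure: events on treatment and up to 30 days after it. A dosed participant with a Grade 3 event who is later judged ineligible would nevertheless appear only in an appendix.

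For SVR12, an eligible-only set is a legitimate prespecified choice. Without an all-treated figure beside it, however, the reader cannot see whether exclusions mattered. The trial is open-label, the core team reviews HCV RNA routinely (SAP 2.7.1), and SAP 2.8 does not say that ineligibility must be judged on pre-treatment data alone. That is a reason for transparency. It is not a claim that any exclusion was driven by outcome.

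SAP Version 2.0 covers 7 participants and is meant to feed a joint manuscript (introduction and 4.3.1). At that size each exclusion changes the printed counts, and the SAP does not say whether the appendix would accompany the safety count into the manuscript.

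**Working it through.** **Population, section by section.**

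| Output | Population named in its own section | Population that applies |
|---|---|---|
| Primary safety count, SAP 4.3.2 | none | eligible and treated (SAP 2.8) |
| Adverse event tables, SAP 4.2.1 | none | eligible and treated (SAP 2.8) |
| SVR12, SAP 4.3.1 | none; missing data counted as failure | eligible and treated (SAP 2.8; protocol 9.1 and 9.6) |
| All-treated SVR12 | not specified | – |

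The protocol settles the set for SVR12. For safety, the 9.6 safety paragraph is silent and 9.2.1.2 is framed by time on and after treatment, but the general statement in 9.1 can be read as covering safety too.

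**Method.** The Wilson interval for x events in n, with p = x/n, is

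[p + z²/(2n) ± z·√(p(1−p)/n + z²/(4n²))] / (1 + z²/n),

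with z = 1.645 for 90% and z = 1.96 for 95%.

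**The plan's own figure.** Take 18/20 from protocol Table 9-1, with z² = 2.706:

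- Divisor: 1 + 2.706/20 = 1.1353.
- Centre: (0.9 + 2.706/40)/1.1353 = 0.852.
- Half-width: 1.645 × √(0.09/20 + 2.706/1600)/1.1353 = 0.114.
- Interval: 73.8% to 96.6%, as printed.

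All seven rows of Table 9-1 reproduce, so no stated figure is in error.

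**Inputs for the illustrations.** The total of 7 enrolled is from SAP 2.1. Three inputs are assumptions: arm sizes of 3, 4 and 5, one treated participant found ineligible, and that person's outcome.

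**Safety, 95% Wilson (level from protocol 9.6), the excluded person having the only event.** For 1/4, z² = 3.8416:

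- Centre: (0.25 + 3.8416/8)/(1 + 3.8416/4) = 0.372.
- Half-width: 1.96 × √(0.1875/4 + 3.8416/64)/1.9604 = 0.327.
- Interval: 4.6% to 69.9%.

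For 0/3 the upper limit is z²/(n + z²) = 3.8416/6.8416 = 56.1%.

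| Assumed arm | All treated | Eligible only |
|---|---|---|
| 3 | 1/3 = 33.3% (6.1 to 79.2) | 0/2 = 0% (0 to 65.8) |
| 4 | 1/4 = 25.0% (4.6 to 69.9) | 0/3 = 0% (0 to 56.1) |
| 5 | 1/5 = 20.0% (3.6 to 62.4) | 0/4 = 0% (0 to 49.0) |

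The shift can also go the other way. If the excluded person in an arm of 4 had no event, 1/4 (25.0%) becomes 1/3 (33.3%).

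**SVR12, 90% Wilson.**

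| Set | All treated | A failure excluded | A responder excluded |
|---|---|---|---|
| Assumed arm of 4 | 3/4 = 75.0% (35.6 to 94.2) | 3/3 = 100% (52.6 to 100) | 2/3 = 66.7% (25.4 to 92.2) |
| All 7 pooled (illustration only; the plan analyses by arm) | 6/7 = 85.7% (54.8 to 96.7) | 6/6 = 100% (68.9 to 100) | 5/6 = 83.3% (49.8 to 96.2) |

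At the planned 20 per arm, excluding one failure would turn 17/20 (85.0%; 67.8 to 93.8) into 17/19 (89.5%; 72.7 to 96.5). The lower limit would then cross the 70% that protocol 9.4.1 treats as acceptable.

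**The case against.** The strongest reply is that the rule was prespecified. Safety is a primary objective, protocol 9.1 describes one primary analysis set, and the paragraph before it names safety and tolerability beside virologic response. Reading 9.1 as covering both outcomes is natural, so the SAP does not depart from the protocol. That stands in full for SVR12. For safety it stands as one plausible reading, so a change needs a dated record.

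The second reply is that nothing is hidden. SAP 2.8 provides the appendix, 4.1.3 describes each exclusion and attributes it to screening errors, eligibility violations are a component of the monitoring committee's report (3.1), and genotype eligibility rests on a pre-entry result (protocol 4.1.7). These are real safeguards, and a reader of the full report could rebuild the safety count. They describe exclusions, however, without putting the person back into the reported count.

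Third, no ineligible participant is shown, and SAP Version 2.0 lists no intervals for the safety endpoint, only a number. Both are true. The safety intervals above therefore show scale and are not planned outputs. Changing the safety set after accrual closed in an open-label trial also has a price. Adding an all-treated line would give the same information, but an endpoint defined by exposure is better counted in everyone exposed.

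**Conclusion.** The concern holds as a minor point. Under SAP 2.8 a treated participant later found ineligible is in neither part of the primary safety count, and the SAP text available (through 4.4.4, without the appendix tables) specifies no all-treated SVR12.

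With 7 participants, one such case could move a safety proportion from 25.0% to 0%, or SVR12 from 75.0% to 100% or 66.7%, in an assumed arm of 4. Those sizes rest on an assumed arm split and an assumed exclusion. If nobody was ineligible, the two sets coincide and no number changes. The documents do not contradict each other on SVR12, no stated figure is wrong, and no bias has been shown.

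**What to change.** 1. In SAP 2.8, 4.2.1 and 4.3.2, base the primary safety endpoint and the adverse event tables on all participants who took at least one dose. Record this as a dated change, because protocol 9.1 can be read as applying the eligible-only set to safety and SAP Version 2.0 postdates closure to accrual.
2. In SAP 4.3.1, keep the eligible-and-treated SVR12 analysis as primary. Add an all-treated row by arm, with the same 90% Wilson and 95% Clopper-Pearson intervals. If nobody was found ineligible, replace the row with one sentence saying that the two sets coincide.
3. Optionally, state in SAP 4.1.3 that ineligibility is judged only on pre-treatment data, and list the reason and timing of each decision. Give the timing as study week, since SAP 2.8 keeps dates out of listings.

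The cost is a few sentences, at most one extra SVR12 row, slightly more analysis work and possibly slightly less favourable figures. The protocol's primary SVR12 population is unchanged.

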2.9 Statistical Methods

For binary or categorical measures, number of participants and percent will be provided.

SAP Version 2: Two-sided 90% Wilson confidence intervals are provided for the key HCV virologic endpoints, per protocol. In addition, two-sided 95% Clopper-Pearson confidence intervals will be provided for SVR12, as suggested by the Gilead statistician on the Jan 6, 2017 manuscript call. For the continuous measures, median, lower and upper quartiles (Q1 and Q3), min, max will be provided. Additional summary statistics, such as mean with standard deviation (SD) may also be included for some measures, if noted below.

3 Components in the Reports

The listed components are described in Section 5.

3.1 SMC Review Reports

The purpose of SMC review reports is to provide data summaries relevant for interim reviews to ensure participant safety and to review data quality and study conduct. As described in the Study Monitoring Plan (SMP), the Open Report will be pooled across study arms, and the Closed Report will be by study arm.

SAP Version 2: There was one SMC review on August 18, 2016. The SMC became aware of the early enrollment closure. An abbreviated SMC report was generated and distributed, in consideration of only 7 participants in the study.

5.1.1 Study History

4.1.2 Accrual

4.1.3 Eligibility Violations and Registration Errors

4.1.4 Baseline Characteristics

4.1.5 Study Treatment Status and Duration of Treatment (Only in the Closed Report)

4.2.1 Adverse Events and Protocol-Required Laboratory Tests

4.2.2 Pregnancy

4.2.3 Deaths

4.2.4 HIV-Related Measures and Changes in ARV Regimen (Only in the Closed Report)

